## D. School Engagement and Recruitment

Our first aim is to engage and recruit elementary schools from two communities on the Navajo Nation for the randomized control trial of the Yéego! Healthy Eating & Gardening intervention. We recognize that personal interactions with key stakeholders is an essential part of community engagement. This will require the assistance of “key influential” in the school system, faculty educators at Diné College, and local residents who are Navajo members of our research team. Based on our previous experience in recruiting of organizations for group-randomized trials, we plan to implement the following steps to recruit and engage potential schools as research partners. In defining the population of schools from which to recruit, we note there are about 90 elementary schools in the Navajo Division of Education system, including 16 in Shiprock and 11 in Tsaile. We will identify schools in Tsaile and Shiprock who meet the eligibility criteria for the study. The eligibility criteria will include having been in existence for at least three years, school size (have between 40 to 100 students in grades 3 and 4 combined), have more than two-thirds Navajo students and satisfy a garden site checklist that can overcome garden barriers (e.g. have access to water) (Figure 2). Information about potential schools will come from the initial phone screening and a school questionnaire. Each school will be contacted by phone and letter to assess their initial interest in participating in the study. After initial conversations, study staff will arrange a meeting with school faculty meeting to discuss the intervention and study procedures in detail. The meeting will provide detailed information on the student recruitment and data collection process and emphasize efforts to minimize disruption of daily classroom routine. For interested schools, we will also do an initial assessment of the school resources and garden site. From these meetings we hope to identify at least six schools, three in each community for further engagement. Our next phase with the schools will serve as a “run-in” period to the trial. During this time we will hold meetings with teachers and parents, and conduct initial surveys to gauge their level of interest, ability to engage in the types of evaluations used in the main study, and likelihood of engaging fully in the curriculum and school garden intervention. Our goal is to randomize a minimum of four schools (two in each community) that will participate for the duration of the project. If all schools qualify for the study on completion of run-in, we will randomize all six schools, two to intervention and four to delayed intervention.

## IV. INTERVENTION AND ASSESSMENT

### A. Yéego! Healthy Eating & Gardening Intervention

Our intervention has two main components: a school garden and a healthy eating and gardening curriculum for students. It also has an ancillary component: family workshops to promote healthy eating and gardening at home. The theoretical framework for the intervention draws on the Social Ecological Model, which states that there are determinants at multiple levels that influence health behaviors, including the social and physical environment, organizations, and family. We have also incorporated Social Cognitive Theory, which states that environmental factors influence individuals and groups, but that individuals and groups can also influence their environment and regulate their own behavior. The school garden is an environmental feature that reinforces the skills, knowledge and behaviors taught in the curriculum, which in turn promote the collective efficacy of the students and their families to maintain healthy eating and gardening behaviors.

**School Gardens.** At each school, we will establish a school garden following guidelines outlined by Life Lab and previous school garden projects. Ideally, school gardens will be located in a highly visible location in full sun, near a water source, fenced within a school play yard and accessible to the central school building, as well as school staff, students and family members. Gardens will consist of four durable raised garden beds (approximately 24 square feet each) filled with amended soil. The region is semi-arid so we will install appropriate irrigation systems that utilize available water resources efficiently including drip irrigation and rainwater harvesting. The garden will serve as a place for school staff and students to garden,

**Figure 2: Garden Site Pre-intervention checklist:**

- Supportive leadership and staff (for developing a garden)
- Staff and volunteer interest in conducting garden maintenance
- Garden site near the main school building(s)
- Access to water at the garden site
- Fencing and/or security for the garden or school to prevent animal browsing and vandalism

as well as an additional outdoor classroom for both student lessons and family workshops. The school will have primarily responsibility for maintaining the garden. However, they will receive technical assistance from the study team throughout the growing season related to planning, planting, maintaining and harvesting what is grown during the school year. We will continue to assist during the summer (between Years 2 and 3), when students and teachers are on summer break. However, we will encourage schools to identify staff or volunteers who can assist with maintenance during the summer months. Plant selection will include vegetables that have grown well in our previous garden projects and informed by staff, student and family preferences. We envision a combination of cool season (e.g. leafy greens like kale and root crops, potatoes, onion) and warm season crops (fruiting crops) like tomato, chili pepper, and the “Three Sisters”: Navajo corns, squashes, and beans. As crops mature and are harvested, research staff and students will measure the garden yield by weight and counts, in order to assess how much the garden space can produce. The fruits and vegetables harvested from the garden will belong to the school. Many Navajo schools provide breakfast, lunch and a snack to their students. We will work with cooking staff to ensure that they can use the produce harvested from the garden for meals and snacks provided by the school. Teachers will also be encouraged to use the garden and its contents (social, insects, plants) as a teaching space for other subjects. Garden infrastructure and plant names with their culinary/medicinal/traditional uses will be posted on signs in both Navajo and English.

**Table 5. Healthy Eating Curriculum**

Unit	Learning Objectives	Example Activity
1. Introduction & Kitchen Safety	Kitchen safety Define personal and community health	Practice kitchen safety skills Prepare and decorate journals
2. Food Sovereignty	Explain food access and availability Read a recipe to create a snack	Community guest speaker to teach significance and prep. of kneel down bread
3. Whole Foods & Nutrition	Identify whole and processed foods Choose healthy food options	Prepare snack from a recipe Analyze food labels and images
4. Empty Calories	Choose healthier sweeteners and low sugar drinks	Taste test varieties of same drink with different sweeteners
5. Fruits and Vegetables	Identify different fruits and vegetables and understand why them is important Recognize My Plate	MyPlate drawing activity Practice knife skills
6. Fiber	Identify strategies for incorporating more fiber into diet with fruits and vegetables	Compare seed anatomy
7. Traditional Foods	Identify traditional foods and their nutritional or medicinal importance	Community guest speaker will teach significance and prep. of blue corn mush Draw and press plants and herbs into notebook
8. Food and Family	Share foods and traditions from their family Learn to double a recipe for a group	Read “Who’s in my family” about different family structures
9. Garden to Table	Describe participants and steps in a community food system	Prepare a snack with local and seasonal ingredients, discussing where they came from
10. Breakfast and Lunch	Understand the importance of making healthy food choices at home and school	Use kitchen skills to help prepare foods for lunch or snack at school
11. Celebrations and Gatherings	Prepare healthier meals for celebrations and gatherings	Practice using a cookbook to find and prepare a recipe for next garden celebration
12. Garden Celebration	Plan and lead a harvest celebration Redefine personal and community health based on what they’ve learned	Harvest and prepare foods from the garden for a celebration with the school community

**Healthy Eating and Gardening Curriculum.** We will provide schools with our curriculum (developed and implemented in our current pilot study) for both healthy eating and gardening that covers the entire school year. Each content area consists of 12 lessons throughout the year and coordinated with the growing season (See Tables 4 & 5, total of 24 lessons). Lessons will be scheduled based on input from school staff, but will occur approximately two times per month. The curriculum was designed based on both formative research with the target population, previous school garden interventions, investigator expertise in theory-based interventions to promote healthy eating and gardening, and instructional design. The curriculum draws on Social Cognitive Theory, which posits that self-efficacy and observational learning are critical for promoting self-regulation and maintaining healthy behaviors. The curriculum meets N.M state standards in health education, science, and

social studies for grades 3 and 4. By integrating the lessons into regular classroom activities, the interventionist can also help with required student assessment (i.e. pre/post learning) demonstrating growth relative to the state standards.

Lessons will be co-led by our interventionist and a teacher from the school as part of the regular school day, consisting of about 45 minutes for each lesson. Our curriculum is focused on children in third and fourth grade. Lessons will be implemented for both grade groups on the same day, but at different times, according to the teachers' schedules. This will allow for smaller groups and a lower teacher to student ratio.

For the healthy eating curriculum, each lesson consists of an introduction to the topic, an activity that addresses the learning objectives for the lesson, snack preparation, writing tasks associated with their garden notebook, and a handout with the day's recipe for the students to take home (Table 5). Lesson structure for the gardening curriculum is similar but includes time for garden maintenance in place of the snack preparation (Table 6). Each lesson aims to increase student self-efficacy in performing gardening and healthy eating-related behaviors, through demonstration and activities. Self-regulation and healthy behaviors are reinforced by observational learning and opportunities to practice the desired behavior (e.g. weeding, food preparation). Students will receive a handout based on the lesson content that can be taken home, so that families are aware of what their student is learning and have information to start or maintain their own gardens. Many of the lessons incorporate reading from children's books that were chosen based on their relevance to Navajo culture and/or the content of the lesson.

**Teacher Curriculum Discussion Groups.** Third and fourth grade teachers from Shiprock and Tsaiile area schools will be invited to participate in a group discussion on how to enhance the existing curriculum for the current study. Teachers will have the opportunity to provide feedback on how best to integrate Diné and AZ/NM state standards into the curriculum and provide suggestions for new content or materials needed to facilitate the curriculum within their schools. Teachers that attend the group discussion will be provided with light refreshments and receive \$30 for their time. At the end of the academic school year, 3rd and 4th grade intervention teachers will be contacted for a 60-minute phone interview to learn about their perceptions of the Yéego! Healthy Eating and Gardening curriculum. The goal is to seek to improve the curriculum through understanding teacher perceptions of what worked well, what needs improvement and what additional support is needed for future implementation. It will also help to understand how delivery of the intervention contributes to study outcomes. Teachers will receive \$30 for their time.

**Table 6. Gardening Curriculum**

Unit	Learning Objective	Example Activity
1. Planning a garden	Use seed packet information Understand how sun affects garden design	
2. Sowing and transplanting	Follow garden plan Use proper technique for planting seeds	Make garden plan. Make garden labels in English and Navajo
3. Garden maintenance	Perform weeding, watering and thinning Identify common weeds Explain what is needed to make a plant grow	Read "Corn is Maize". Model and have students practice weeding and watering
4. Water	Describe the water cycle, and how humans impact it. Explain how water quality affects human health	Read "Snail Girl Brings Water: A Navajo Story" Model the water cycle.
5. Compost	Explain why compost is important	Collect compost samples and examine them with magnifying glass. Record observations.
6. Plant anatomy	Identify plant parts and function Describe traditional uses and cultural significance of traditional craft	Harvest and classify plants. Plant scarlet runner beans in observation cups.
7. Traditional gardening practices	Describe traditional growing and farming practices and how they related to food sovereignty	Hear about traditional growing practices from local community member Implement one traditional garden practice
8. Pollination	Explain how pollination, fruit and seeds are linked Describe how and why to manage pests	Read "Zinnis, or How the Corn was Saved." Plant wildflowers.

9. Seasonal crops	Understand how seasons affect plants Describe how home and school gardens help localize the food system	Create garden calendars. Observe seed and plant growth.
10. Native plants and ecology	Identify native plants and describe their traditional uses	Plant native plants in the garden
11. Food presentation and seed saving	Describe methods for food preservation Identify food safety considerations	Quick pickle vegetables for a snack. Create seed packets for saved seeds.
12. Harvest	Measure amount of produce harvested Practice safe food storage and preparation	Weigh harvested produce and compare across garden plots using a bar graph.

**Family Workshops.** In the second year of the intervention (Year 3), there will be quarterly healthy eating and gardening workshops for family and community members to attend. These events will focus on engaging school staff, students and their families in the garden and provide an opportunity for families to learn gardening and healthy eating topics together. They will also be open to the entire community (Shiprock or Tsai), in order to help promote positive social norms about healthy eating and gardening. For this reason, this component is considered ancillary, and will be evaluated separately from the main intervention components, by tracking attendance. Each workshop will focus on a specific skill that families can use at home to either grow or prepare healthy food. Participants will also receive small prizes for attending, such as plants, gardening tools, seeds or cooking utensils. These events will be based on similar events conducted during our pilot of the school-based intervention that were well attended and well received by the Shiprock community.

**Due to COVID-19 Family Workshops Go Online.** Due to the Navajo Nation, New Mexico, and Arizona responses to the COVID-19 pandemic, the planned in-person family workshops have pivoted to a video workshop series. The series is housed on the NMSU Agricultural Science Center website. The “how to” workshop series provide family and community members the opportunity to learn about gardening and healthy eating through a short video. The video series includes:

1. Raised Bed Construction (with media mixes)
2. How to Make Blue Corn Mush (from healthy eating curriculum activity)
3. How to Make Apple Donuts (from healthy eating curriculum activity)
4. Planting Peach Seeds
5. Transplanting Nursery Fruit Trees
6. Fruit Tree Pruning
7. Cool Season Crops
8. Seed Saving/Storage
9. Tunnel Construction
10. Frost Cover/Row Cover/Plastic Mulches (with ways to purchase resources)
11. Navajo Spinach Food Preservation

Videos are filmed by NMSU Agricultural Science Center staff, Diné College Extension Agents, Extension Agents from the San Juan County Cooperative Extension, Utah State University. The original workshops and the video workshop series are designed to be open to the entire community. Accordingly, the videos will be promoted and uploaded to the NMSU Agricultural Science Center website <https://farmingtonsc.nmsu.edu/>, an open-access public website. The NMSU website is maintained by the main NMSU campus in Las Cruces New Mexico, [name] will be the direct contact. Student participants in the Yéego! Healthy Eating and Gardening Project will receive a promotional e-flyer through their school announcing the video series.

#### **Video Production Timeline:**

#### **B. Data Collection/Assessment**

After the end of the run-in period, we will obtain assent and consent from parents of children in the participating schools that are eligible to be randomized. This assent and consent will be for all the study assessments during the entire study period. In Year 2, we will survey the children and a parent (or index adult caregiver) at baseline (T1) which is at the beginning (August) and at follow-up (T2) which is at the end (June) of the school year. Timing of assessments will be staggered so that presence in the school at any one time point will occur on non-consecutive days, to minimize disruption in the classroom. Data assessment is quite

time consuming since the surveys have to be read to the respondent in an interview format conducted individually. We will use electronic data collection methods to capture the responses from both the interviewer-administered survey and from a culturally adapted virtual picture sort method. Response options will be bar-coded on a screen displaying the picture of the groups of foods.

Prior to the start of the school year, and after a successful run-in, information regarding the study will be sent out to all families in randomized schools. They will also be invited to attend an information night timed to coincide with a parent orientation or chapter house meeting to learn about the study in detail. Information about the study will also be visible in the school newsletter prior to the start of recruitment, posted on school websites and posters displayed at the school to invite students to participate in the study. The project will ask from the school administration staff the first and last name of students, grade and teacher in order to create individualize recruitment packets. Students will receive a recruitment packet from their teacher to be sent home with their daily schoolwork. The packet will include information about the study, child assent and adult caregiver permission and self-consent to participate in the study. Students will be encouraged to return their packets in one week to be eligible for a school-wide raffle. Raffle for past studies included gift certificates to a local restaurant, movie theatre or activity for the family. The top raffle prizes will be a \$50 gift card for the family, additional prizes include tote bags and backpacks. After the first week, a second round of packets will be distributed to the remaining students to reach the required recruitment goal of 60% of third and fourth grade students. In addition, to compensate teachers for their support of the packet process, classes that reach the 60% enrollment goal will receive \$50 worth of classroom teaching supplies. The teachers will nominate what supplies their classroom will need. Study staff will purchase the items up to \$50 and deliver to the teachers. For the students consented to participate in assessment, study staff will identify a series of after school times for students to complete the baseline survey. Student and adult caregivers who are not able to attend an assessment session after school, will be provided the opportunity to conduct the assessment at their home or place of their choosing. Each student/adult pair completing the assessment will receive a monetary gift in the form of cash, gift card or small gifts for children valued at \$5 (e.g., flashlight, water bottle, cinch-sack/backpack). The starting cash amount for parent survey is \$20 and child is \$5. In order to maximize retention at later time points the survey incentive will increase by \$5 at each time point. Other retention efforts include phone, email and text reminders. A school champion for each school will be assigned by the principal to assist with enrollment and assessment logistics for each school. The champion coordinates times for the assessment team to pick up completed enrollment packets, deliver new packets to teachers and assist with delivery of raffle prizes to schools and families. As a token of appreciation for their assistance, an honorarium of \$100 will be provided at the end of the 2020 and 2021 school year.

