### Parent/guardian survey.

There are four methodologies for completing the parent/guardian survey.

1. From the consented family, the parent completed the baseline survey and is available to complete the FU survey.
2. From the consented family, the parent consented, but did not complete the baseline survey. They will be invited to complete the follow-up survey.
3. From the consented family, the parent completed the baseline survey but is unable to complete the FU survey at any time in the follow-up window (T2 is April-May 2020).
4. A 3rd or 4th grader or their family are requesting an opportunity to participate at follow-up but have not yet completed the family packet or consent or assented their child.

1. The assessment coordinator will contact the parent who completed the baseline (the index parent/guardian) to again participate in the follow-up surveys (T2, and later T3).
2. The assessment coordinator will contact the parent who consented to the baseline but did not complete the survey (the index parent/guardian), to participate in the follow-up surveys (T2, and later T3).
3. If it is found that the index parent/guardian is not able to complete the survey, a new index parent/guardian can be appointed. The new index parent/guardian will be contacted to complete *Parent Survey and Verbal Participation Consent Form* approved by IRB. The verbal consent will be read and must be verbally affirmed by the parent/guardian prior to completing the parent survey interview. At the top of the parent follow up survey, there is a space for the interviewer to note change in survey completer.

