**New Student Enrollment:** New students will not be actively recruited to participate in the study at T2 or T3. If the new student or their parent wishes to participate on their own accord, they can request an enrollment packet from their teacher. In this way, students enrolled at a participating school in the 3rd or 4th grade after the baseline assessment was completed will have the opportunity to participate in the assessment. The first step is for them to take home the enrollment packet for their parent/guardian to complete. The child cannot participate in the survey without a completed packet. As before, the packet will include information about the study, child assent and adult caregiver permission and self-consent to participate in the study, and a Parent Family Survey (all documents IRB approved – see section VI List of Approved Documents). The student and parent/guardian must complete the enrollment documents and return the sealed packet to the teacher. The teacher will give the sealed packets to the school designated school champion to be securely locked in the assessment file cabinet until retrieved by the study staff. Procedures for obtaining student follow-up survey and parent follow-up survey will follow similar steps to those used at the baseline survey.

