## E. Analysis Plan

Two of our four primary outcome measures in children (tendency to choose fruit and vegetables to eat during snacks/meals and gardening self-efficacy) will be measured through questions that use a Likert-type scale with four response options. With numeric codes assigned to each response option, means and standard deviations will be calculated per question and overall. Thus, possible mean values range from one to four. The intention to treat analysis will be a t-test comparing the change in mean values from baseline (beginning of school year at T1) to follow-up (end of school year at T2) in the intervention schools to those changes in mean values in the schools receiving the delayed intervention. This differential change in groups between T1 and T2 is the estimated intervention effect. The estimated effect of the intervention will also be analyzed using linear mixed models with T2 individual outcome as the dependent variable and intervention assignment as the

independent variable, adjusting for T1 individual outcome and school random effect. It will also allow for adjustment for additional covariates (school within intervention group if applicable) and for known or probable individual level confounders. Information from all responding students will be included in the analysis, with adjustment for repeated measures (expected to be the majority of the students). This will assess robustness of inferences from the simpler model. A sensitivity analysis without adjusting for possible intra-school correlations will be performed using linear regression models. In addition, the Akaike Information Criterion will be compared between the simpler model and the theoretically correct multilevel model to check model fit.

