### **C. Study Approach Documents & Intervention**

1. School Information Sheet – approved 7/3/19
2. Assessment Overview Document – approved 7/3/19
3. Recruitment packet documents – approved 7/3/19
  - a. Intervention Later Information Sheet
  - b. Intervention NOW Information Sheet
  - c. Parent Instruction Sheet
4. Study Logo – approved 7/11/2019
5. Principal Support Letter template – approved 7/11/2019
6. Intervention Curriculum – approved 8/12/19

7. Follow up Assessment Parent/Guardian Postcard – approved 01/16/20
8. Follow up Assessment Child/Student Postcard – approved 01/16/20
9. Follow up Assessment Parent/Guardian Call Script – approved 01/16/20
10. Revised Intervention Curriculum Part I – approved 1/28/20
11. Revised Intervention Curriculum Part II – approved 3/12/20
12. Family Update Letter – COVID-19 – approved 3/19/20

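### Do arm-aware enrolment and children who join at T2 require a new rule in the analysis plan?

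*Combined protocol and SAP*

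**What the plan says.** **Order of randomisation and recruitment.** Sections III.A and III.D place randomisation of schools at the end of run-in. Section IV.B then says "information regarding the study will be sent out to all families in randomized schools", followed by packets sent home through teachers; section V.B repeats this. The recruitment packet documents in section VI.C include an "Intervention NOW Information Sheet" and an "Intervention Later Information Sheet". Another sentence in section IV.B points the other way: it describes consent for "children in the participating schools that are eligible to be randomized", which reads as consent before allocation. The date of randomisation is not given.

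**Late entry.** The Parent/guardian survey section foresees a third or fourth grader or family "requesting an opportunity to participate at follow-up but have not yet completed the family packet", and gives the follow-up window as "T2 is April-May 2020". The New Student Enrollment paragraph rules out active recruitment at T2 or T3 but adds: "If the new student or their parent wishes to participate on their own accord, they can request an enrollment packet from their teacher".

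**Analysis.** In section IV.E the intention-to-treat analysis is a t-test on the T1-to-T2 change. A linear mixed model with the T1 outcome as covariate and a school random effect checks its robustness. For that model, "Information from all responding students will be included in the analysis", with an adjustment for repeated measures that is expected to concern most students, though not all. For the healthy eating score and gardening at home, the section names only a t-test and a z-test on differential change.

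**The concern.** The primary outcomes are children's own reports of food choice, eating, gardening and confidence. If families knew the arm before T1, two things could follow. Enrolment could differ by arm, or T1 answers could be shifted by anticipation. A shift at T1 feeds straight into a change score. The T1-adjusted model removes only part of it, so the two planned analyses can disagree, and no rule says which then prevails. In some cases both err in the same direction, and their agreement would then reassure wrongly.

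Children who join at T2 choose to enter after allocation and after months of lessons. If they counted in the T2 means but not the T1 means, the comparison would no longer be of the same children over time. The plan includes all responders in a model that needs a T1 value, and does not say how the two fit together. At stake are a biased effect estimate of unknown direction and a choice between estimates made after seeing results.

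**Working it through.** **The protocol's own figure.** Section V.A anticipates up to 960 participants: 80 children × 6 schools × 2 (child plus adult) = 960. It reproduces. The documents give no intraclass correlation (ICC), T1–T2 correlation or joiner count, so those below are assumptions.

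**1. Bias if T1 is shifted.** Let intervention schools be shifted by d at T1, let a fraction k of the shift persist at T2, and let r be the T1–T2 correlation. With equal SDs the biases are: T2-only comparison kd; T1-adjusted (k − r)d; change (k − 1)d. For d = 0.2 SD and r = 0.3 to 0.7:

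| k | T2-only | T1-adjusted | Change |
|---|---|---|---|
| 0 | 0 | −0.06 to −0.14 | −0.20 |
| 0.5 | +0.10 | +0.04 to −0.04 | −0.10 |
| 1 | +0.20 | +0.14 to +0.06 | 0 |

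The two planned estimates differ by (1 − r) × 0.2 = 0.06 to 0.14 SD. On the fruit and vegetable choice score (SD 0.48, section IV.C) that is 0.03 to 0.07 points. When k is below r, both err in the same direction. The algebra is therefore right, but d and k cannot be learned from this trial.

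**2. Chance gaps at T1.** Take 2 against 4 schools (section III.D) with 48 children each (the 60% recruitment goal of section IV.B applied to 80). The SD of the gap is √[(ICC + (1 − ICC)/48) × (1/2 + 1/4)].
- ICC 0.01: 0.152 SD; P(gap of 0.2 SD or more) = 0.19
- ICC 0.02: 0.174 SD; 0.25
- ICC 0.05: 0.229 SD; 0.38

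A school-level test (4 df) detects a true 0.2 SD shift with power of only 0.18, 0.15 and 0.11. A T1 gap would be unremarkable, and its cause could not be identified.

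**3. T2 joiners.** The shift in one arm's T2 mean is the share of joiners times their difference from the rest: 0.05 × 0.3 = 0.015 SD up to 0.15 × 0.5 = 0.075 SD. That arises only if joiners are counted. A joiner has no T1 value, so has no change score and contributes nothing to a model with T1 as covariate.

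**4. What a stricter rule would do.** The natural remedy is to add the T2-only comparison, call an effect robust only if T2-only and change agree, and otherwise report the interval between them.
- *Coverage.* With no T1 shift, the probability that this interval contains the true effect is arccos(√((1 − r)/2))/π: 0.30 at r = 0.3, 0.33 at r = 0.5, 0.37 at r = 0.7. With d = 0.2 SD and k = 0, 0.5 or 1 (ICC 0.01 to 0.05), simulation gives 35% to 59%. The interval brackets the effect in expectation only, because it ignores sampling error.
- *Power.* Assume an effect of 0.4 SD, ICC 0.02, r = 0.5, no shift and school-level tests at p < 0.05. Power is 0.42 for change, 0.52 for T1-adjusted (r taken as known), and about 0.23 when T2-only and change must both be significant.

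**The case for a change.** The strongest case for a change runs as follows. Separate now and later sheets in a recruitment packet are hard to explain unless families were told their arm. T2 is still ahead in the text, so a rule fixed now would stop the choice of estimate from following the results. The mixed model is offered as a robustness check, yet it can agree with the t-test when both are wrong in the same direction: at d = 0.2 SD, r = 0.5 and k = 0.2, adjusted is −0.06 SD and change −0.16 SD. Two of the four primary outcomes have no T1-adjusted model named at all.

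Much of this stands as description. Arm awareness is likely, though inferred from titles and one adjective: the sheets' text and the design figure are not available, and the consent sentence in section IV.B conflicts. The wording on children without a T1 value is loose, and no rule covers disagreement between the two analyses.

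It does not stand as a reason to amend. To say the plan ignores a T1 gap goes too far, since change from T1 and adjustment for T1 both deal with a measured one. No analysis of these data can separate anticipation from chance with six schools. The rule that would close the same-direction case roughly halves power and sets aside the T1-adjusted estimate, the most powerful of the three in that example. It would also need its own definition of when two estimates support the same conclusion.

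**Conclusion.** No change to the plan follows.

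- **Arm awareness at T1.** Probable, of unknown size and direction, and past correction because T1 has been collected. Once lessons and a garden start, the trial cannot be masked in any case. The conflicting sentences on consent and randomisation are a drafting matter. Dates, enrolment by arm and T1 values by school belong in the report; setting them out changes no estimate.
- **T1 gap.** Addressed by both planned analyses, which differ by 0.06 to 0.14 SD for a gap of 0.2 SD. Reporting both, as planned, shows any disagreement. A rule requiring the T2-only and change analyses to agree would cost power (0.42 to about 0.23 in the example) for no sound gain in coverage.
- **T2 joiners.** A gap that analysts fill sensibly by using children with a T1 value and describing joiners apart. Few are likely: they are not actively recruited, and the amended T2 effort (Follow-up survey delivery) is aimed at those who completed baseline. If they were counted, the effect would be about 0.015 to 0.075 SD.

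These sizes rest on assumed d, k, r, ICC and joiner shares. The joiner conclusion would weaken only if joiners were numerous and very different: at 20% of one arm and a full SD apart, the shift would be 0.20 × 0.48 = 0.096 points on the choice score.
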